	
Until recovery of platelets and ANC, hematology assessments are done as often as necessary to determine the exact date of recovery of platelets and ANC.
 
Safety laboratory assessments include complete blood count, time to recovery of platelets $\geq 50 \times 10^9/L$ and $\geq 100 \times 10^9/L$, ANC recovery $\geq 0.5 \times 10^9/L$ and $\geq 1.0 \times 10^9/L$, clinical chemistry, including liver function test, coagulation, and 12-lead electrocardiogram as well as cardiac ultrasound.

Statistical considerations
	
Primary Efficacy Parameter The primary efficacy measure will be the rate of complete responders (CR).
 
Secondary Efficacy Parameters The secondary efficacy measures:
 
 • Rate of partial remissions • Percentage of patients being transplanted after induction therapy • Early death rate 
will be analyzed as rates.
 
 • Overall survival (OS); • Event-free survival (Events are defined as Death, not achieving a CR or CRi, Relapse after CR or CRi) 
will be described by median survival time and respective 95%-confidence intervals.

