¹⁹ Follow-up is to include all patients, including those having undergone SCT

²⁰ required at screening and if clinically indicated during the treatment phase. Ophthalmologic examination includes:

- prior to dilation: best corrected visual acuity and slit lamp examination including tonometry
- following dilation: fundoscopy and a slit lamp exam to document lens clarity. If a cataract is seen during the exam, cataract will be graded according to the Lens Opacities Classification System III (LOCS III)

²¹ Hematological Recovery status: platelet recovery $\geq 50 \times 10^9/L$ and $\geq 100 \times 10^9/L$, ANC recovery $\geq 0.5 \times 10^9/L$ and $\geq 1.0 \times 10^9/L$ reached and date of recovery. Until recovery of platelets and ANC, hematology assessments are done as often as necessary to determine the exact date of recovery of platelets and ANC

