6.4 Concomitant Medication and Treatment

Concomitant medication is defined as any prescription or over-the-counter preparation, including vitamins and supplements. Patients may continue their baseline medication(s). All concomitant medication(s) must be reported in the case report form (CRF). Any diagnostic, therapeutic or surgical procedure performed during the study period should be recorded, including the dates, description of the procedure(s) and any clinical findings. Patients should minimize the use of products containing acetaminophen to less than 1000 mg acetaminophen on dosing days. Acetaminophen can interfere with the metabolism of Selinexor. For combination painkillers containing acetaminophen it is recommended that single agent opiates or aspirin combinations (when clinically acceptable) be substituted.

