6.4.1.2 Use of Blood Products

During the administration of Selinexor, patients may receive red blood cell (RBC) or platelet transfusions, if clinically indicated, per institutional guidelines. Appropriate anti-coagulation is allowed during the study (eg: LMW heparin, direct factor Xa inhibitors, etc).

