7.1.4 NOT to be reported as SAEs

For this study, the following is **not** classified as serious adverse event:

- Progression or deterioration of the malignancy under study (including new metastatic lesions) or death due to progression.
- Hospitalization for the performance of protocol-required procedures or administration of study treatment. However, hospitalization or a prolonged hospitalization for a complication of therapy administration will be reported as an SAE.
- Hospitalization or procedures planned prior to study start. A pre-planned procedure must be documented in the source documents. However, hospitalization or prolonged hospitalization for a complication remains to be reported as an SAE.
- An elective hospitalization for a pre-existing condition unrelated to the studied indication.
- Hospital admission that is not associated with an adverse event (e.g. social hospitalization for purpose of respite care).
- Routine treatment or monitoring of the studied indication not associated with any deterioration in condition.
- The administration of blood or platelet transfusion as routine treatment of studied indication. However, hospitalization or prolonged hospitalization for a complication of such transfusions remains to be reported as an SAE.
- Emergency outpatient treatment or observation that does not result in admission, unless fulfilling other seriousness criteria above.

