8.4.4 Safety Evaluation

Safety evaluation will comprise the following variable and their change from baseline:

- Blood pressure, pulse, temperature
- Physical examination
- Urine analysis
- Hematology
- Clinical chemistry
- Time of recovery of platelets and ANC
- Coagulation tests

The number of patients developing adverse experiences will be tabulated [NCI CTCAE] Version 4.03. The CTC v4.03 will be the basis for grading the laboratory changes. Additionally, the subset of adverse experiences considered treatment-related will be summarized. Listings of adverse experiences leading to treatment discontinuation and those identified as 'severe' or of 'maximal' severity will be provided.

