17.6 Appendix 6 – NCI-CTCAE version 4.03

17.7 Appendix 7- Response criteria in AML

Definitions of response criteria are based primarily on those given by Döhner et al.⁽¹⁾

Response criteria	Absolute Neutrophil count	Absolute Platelets count	Bone marrow Blasts (%)	Comments
Complete remission (CR)*	$>1.0 \times 10^9/L$ (1000/ μ L)	$>100 \times 10^9/L$ (100.000/ μ L)	<5	Absence of blasts with Auer rods; Absence of EMD; independence of red cell transfusion
CR with incomplete recovery (CRi) [†]	$<1.0 \times 10^9/L$ (1000/ μ L)	$<100 \times 10^9/L$ (100.000/ μ L)	<5	All CR criteria except for residual neutropenia or thrombocytopenia.
Morphologic leukemia-free state [‡]	NA	NA	<5	Absence of blasts with Auer rods; Absence of EMD; no hematologic recovery required
Partial remission (PR)	$>1.0 \times 10^9/L$ (1000/ μ L)	$>100 \times 10^9/L$ (100.000/ μ L)	5 to 25	Relevant in the setting of phase 1 and 2 clinical trials only; decrease of pretreatment bone marrow blast percentage by at least 50%
Cytogenetic CR (CRc) [§]	$>1.0 \times 10^9/L$ (1000/ μ L) or $<1.0 \times 10^9/L$ (1000/ μ L)	$>100 \times 10^9/L$ (100.000/ μ L) or $<100 \times 10^9/L$ (100.000/ μ L)	<5	Reversion to a normal karyotype at the time of morphologic CR (or CRi) in cases with an abnormal karyotype at the time of diagnosis; based on the evaluation of 20 metaphase cells from bone marrow
Molecular CR (CRm) ⁱ	No standard definition; depends on molecular target			

Treatment failure	
Resistant disease (RD)	Failure to achieve CR or CRi (general practice; phase 2/3 trials); or failure to achieve CR, CRi, or PR (phase 1 trials); only includes patients surviving ≥ 7 days following completion of initial treatment, with evidence of persistent leukemia by blood and/or bone marrow examination

Death in aplasia	Deaths occurring \geq 7 days following completion of initial treatment while cytopenic; with an aplastic or hypoplastic bone marrow obtained within 7 days of death, without evidence of persistent leukemia
Death from indeterminate cause	Deaths occurring before completion of therapy; or < 7 days following its completion; or deaths occurring ≥ 7 days following completion of initial therapy with no blasts in the blood, but no bone marrow examination available
Relapse [¶]	Bone marrow blasts $\geq 5\%$; or reappearance of blasts in the blood; or development of extramedullary disease

EMD extamedullary disease

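### Platelet recovery is defined by count alone while platelet transfusions are allowed, so a transfused count can be recorded as recovery and date it too early

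*Protocol*

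**What the plan says.** Platelet recovery appears in the protocol synopsis (Safety assessment), in 5.1.4, in note 21 to the schedule of assessments, and in 5.2.4 to 5.2.6. Each place gives the same two thresholds, 50 and 100 × 10⁹/L, and nothing else that qualifies the count. Note 21 has sites record whether each threshold is "reached and date of recovery. Until recovery of platelets and ANC, hematology assessments are done as often as necessary". The synopsis states the purpose of the repeated counts: "hematology assessments are done as often as necessary to determine the exact date of recovery of platelets and ANC". Section 5.2.6 continues the recovery assessment in follow-up only until the thresholds are met.

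On transfusion, 6.4.1.2 says that while Selinexor is being given "patients may receive red blood cell (RBC) or platelet transfusions, if clinically indicated, per institutional guidelines". Section 7.1.4 lists among events that are not SAEs "The administration of blood or platelet transfusion as routine treatment of studied indication".

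On use, 8.4.4 lists "Time of recovery of platelets and ANC" as a safety variable, and section 10 includes recovery times in what the DMC reviews. The SAP is silent: recovery time is not among the safety variables in its section 4, has no row in its schedule (19.1) and no table in 19.2. The addendum adds nothing on it.

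In Appendix 7 the comments on CR read "Absence of blasts with Auer rods; Absence of EMD; independence of red cell transfusion". They set a transfusion condition for red cells and none for platelets.

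**The concern.** A platelet transfusion raises the count for a time without any recovery of the marrow. If counts are taken often and the rule looks only at the number, a patient who still depends on transfusion can be given a recovery date. Because intensive counting is required only until recovery, and the follow-up assessment ends when the threshold is met, an early false date can also end the observation that would have shown the true one.

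What is at stake is the description of haematological safety. This is a single-arm trial, so there is no control group with the same bias, and the absolute recovery time is what the DMC and later readers will use. The patients whose dates are open to error are those who needed platelet support, and prolonged thrombocytopenia among them is what the variable ought to show.

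**Working it through.** **Does the plan give a figure to reproduce?** Not for recovery time. The documents contain no expected recovery time, transfusion rate, transfusion trigger or expected rise in count. The check is therefore of the rule, its direction, and what it can and cannot reach.

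**1. The rule.** Inputs: thresholds of 50 and 100 × 10⁹/L (synopsis, 5.1.4, Table 2 note 21, 5.2.4 to 5.2.6); platelet transfusion permitted (6.4.1.2) and routine (7.1.4). None of the recovery sections requires an untransfused count, a transfusion-free interval or a confirmatory second count. A supported count over the threshold satisfies the text.

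**2. The direction.** Let U(t) be the count without support, S(t) ≥ 0 the part due to transfusion, and c the threshold. True recovery is T = first t with U(t) ≥ c. By count alone, recorded recovery is R = first t with U(t) + S(t) ≥ c. Since S(t) ≥ 0, R ≤ T for every patient. Errors cannot cancel.

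**3. The size.** If a fraction f of patients is misdated by an average of d days, the mean is too short by f × d. Neither input is in the documents. Purely as an assumed illustration, take true recovery to 50 at about day 30, a supported count over 50 at about day 12, and f from 10% to 30%:
- d = 30 − 12 = 18 days
- f = 0.10: 0.10 × 18 = 1.8 days
- f = 0.30: 0.30 × 18 = 5.4 days

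In the same illustration 70% to 90% of patients stay at about day 30, so the median does not move. Section 8.4.1 plans both mean and median, so the effect depends on which one is read. These figures show how the error works; they do not estimate it.

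**4. Reach into the primary endpoint.** The plan's cut-off is reproduced first: 25 × 0.30 + 1.645 × √(25 × 0.30 × 0.70) = 11.27, nearest integer 11, plus 1 = 12 responders of 25. The exact binomial one-sided error at 0.30 is 0.0442, and the power at 0.60 is 0.922, against the 0.05 and 0.90 specified. A transfused platelet count can move a patient only between CRi and CR. Both count as responders, so the number compared with 12 does not change.

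**5. Reach into the response categories.** CR and PR both require platelets above 100 × 10⁹/L in Appendix 7. One patient relabelled from CRi to CR changes the CR share by 1/40 = 2.5 points overall, 1/25 = 4 points in the first group or 1/15 = 6.7 points in the flat-dose group. That patient must already meet every other CR criterion, including neutrophils above 1.0 × 10⁹/L and red-cell independence. The PR rate, a secondary endpoint, is exposed in the same way.

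**The case against.** No section says that the first count over the threshold is the recovery date, and investigators may well have discounted counts taken just after a transfusion. That stands, and it is why the claim is that supported counts can be recorded as recovery, not that they were. It does not close the gap: nothing tells sites to discount them, and 5.2.6 stops the assessment once the threshold is met.

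Recovery time is descriptive, with no decision rule attached. That also stands, and it limits the weight of the point.

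The documents give no basis for a particular transfusion-free window, and any window can date true recovery late. If unsupported recovery comes 4 days after the last transfusion, a 7-day rule dates it about 3 days late. This is fair. It argues for fixing the window in advance and showing a shorter one beside it, not for having none.

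A reader might infer that the primary result is inflated, because the synopsis (Statistical considerations) and 8.4.3 name CR alone as the efficacy measure. The documents do not support this. The primary objective and endpoint, protocol 8.1, SAP sections 2 and 6 and the planned response tables all use CR or CRi, and the addendum also counts MLFS as response. No test of a CR-only rate is planned.

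A reader might also conclude that Appendix 7 should be rewritten. Its definitions are based primarily on published expert-panel criteria. Enrolment ended in June 2016, and the addendum reports that an initial analysis had already been done. Changing the response definition now would be a post-hoc departure from those criteria.

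Finally, it is tempting to say that the DMC reviews recovery times because Selinexor may prolong aplasia. The protocol gives no such reason.

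**Conclusion.** The point holds for platelet recovery time. As written, the rule accepts a transfused count, and the resulting error can only make recovery look earlier. It affects a listed safety variable that the DMC reviews, in a trial without a control group. The amount cannot be computed from the documents; the 1.8 to 5.4 days above rests wholly on assumed inputs, and the median need not move at all. The conclusion assumes only that some patients receive platelets before they recover and have a count taken afterwards, which the permission to transfuse and the frequent counting make plausible.

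The effect on response is secondary. The CR/CRi primary endpoint and its cut-off of 12 of 25 are unchanged. The CR/CRi split and the PR rate could shift, but only for patients whose platelet criterion was met through transfusion and who met all the other criteria.

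**What to change.** Make the change in the SAP, as a derivation rule:

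- Date platelet recovery to each threshold as the first count at or above it with no platelet transfusion in a pre-stated preceding interval. Seven days is a reasonable main choice, with 3 days as a sensitivity analysis because the longer window can date true recovery slightly late.
- Add a recovery-time table, overall and by dosing schedule, with a stated rule for patients who die, relapse or go to transplant before recovery. Editing the protocol definitions alone would produce no analysis, because the SAP now plans none.
- Confirm that transfusion dates are in the CRF or source. Section 6.4 says "Any diagnostic, therapeutic or surgical procedure performed during the study period should be recorded, including the dates", but it does not name transfusions. If the dates cannot be retrieved, state in the report that recovery times are by count regardless of transfusion.
- Leave Appendix 7 unchanged. Show the CR/CRi split and the PR rate with a platelet-transfusion condition as a sensitivity analysis only.

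The cost is a few sentences, one table and a check of the data. Recovery times will become somewhat longer. Where a site stopped frequent counts after a supported value, the later date will depend on the next scheduled count, and the report should say so. Treatment decisions and the primary analysis are untouched.

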
Sample size calculation
	
The sample size calculation is based on the evaluation of response rates according to Fleming for single-stage phase II designs. For the Fleming's procedure the two response levels p_0 (expected CR rate) and p_1 (meaningful increase in CR rate) are specified as $p_0=30\%$ and $p_1=60\%$:
 
$N=25$ patients should participate in the study to ensure a power of $1-\beta=0.90$ for the discrimination of p_0 and p_1. According to Fleming the null hypothesis should be rejected if at least
 $r = \left\lceil Np_0 + Z_{1-\alpha} \sqrt{Np_0(1-p_0)} \right\rceil + 1$ 
responses are observed ($\lceil x \rceil$ denotes the nearest integer to). With p_0 and N defined as above and $Z_{1-\alpha} = (1 - \alpha)$-quantile of the normal distribution = 1.645 at least 12 responders should be observed to show the efficacy as postulated.
 
Using the same approach in the 15 additional patients, submitted to an adapted drug regimen, the power will be 80% to discriminate a $p_0=30\%$ (expected CR rate) from a $p_1=65\%$ (meaningful increase in CR rate), if 8 out of 14 completed patients are considered as responders, with a one-tailed alpha error of 5%. Alternatively, the power will be 90% to discriminate a $p_0=30\%$ from a $p_1=70\%$ again if 8 out of 14 completed patients are considered as responders, with a one-tailed alpha error of 5%.

Accompanying baseline translational study (optional)	Leukemic blast cells will be isolated pre- and 24 hr post- a single Selinexor dose (60 mg) given at baseline (after registration and before first induction cycle). Blast cells will be used for leukemic stem cell gene expression profiling and in mouse model studies to define parameters associated with clinical responsiveness to Selinexor.
Data Monitoring Committee	An independent Data Monitoring Committee (DMC) will be implemented that reviews accumulating data of the clinical trial with respect to any potential safety issues, study progress and critical efficacy endpoints. The DMC will be an independent board consisting of 2-3 physicians with special expertise in AML. A physician is not allowed to participate in this clinical trial while serving on the DMC. The DMC will be supported by an independent statistician, if necessary. The DMC will review safety data, recovery times and efficacy of the clinical trial and support the interpretation of clinical trial results.

INFORMATION TO BE PROVIDED REGARDING SAES/PREGNANCY

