No standard regimen exists for the treatment of patients with relapsed acute myeloid leukemia (AML), particularly in patients with a first remission duration of less than 1 year ⁽¹⁶⁾. A number of agents have activity in recurrent/relapsed with an overall response rate of 20-80%, depending on study design and treatment (see Table 1, Appendix 1). Re-induction with Ara-C and daunorubicin will result in a 50% CR rate in patients who had a first remission lasting longer than 1 year ⁽¹⁷⁻¹⁹⁾. In a trial of mitoxantrone in combination with Ara-C in patients with refractory or relapsed AML with 49 patients 62.5% with first relapse AML achieved complete remission while none of the four patients with more than one prior remission responded ⁽²⁰⁾. A triple combination of mitoxantrone, etoposide, and cytarabine (MEC) demonstrated a CR induction rate of 55% in a population including 30 patients with relapsed AML, 28 patients with primary refractory AML, and 16 patients with secondary AML ⁽²¹⁾. A phase 1-2 study of clofarabine plus Ara-C in 25 patients with relapsed acute myeloid leukemia 7 (22%) achieved complete remission (CR), and 5 (16%) achieved CR with incomplete platelet recovery (CRI), for an overall response rate of 38% ⁽²²⁾. For patients not achieving a complete remission the only potentially curative treatment option is allogeneic transplantation with up to 20% of patients being long term survivors ⁽¹⁴⁾.

Therefore, the combination of Ara-C and idarubicin was chosen for standard induction therapy and if the patient receives complete remission transplantation is recommended.

In the light of a dismal prognosis for patients with relapsed/refractory AML a great clinical need exists for new treatment options.

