8.2 Sample Size Calculation

The sample size calculation is based on the evaluation of response rates according to Fleming using the A'Hern (Sample size tables for exact single-stage phase II designs. Statist. Med. 2001;20:859-866.) extension.

In Fleming's procedure two response levels p_0 and p_1 are specified:

- the largest response proportion p_0 which, if true, would clearly imply that the treatment does not warrant further investigations (except for other types of administration, e.g. in standardized combinations); and
- the minimum required response level p_1 that would imply the treatment warrants further investigations.

The following characteristics were specified

- $p_0 = 0.30$
- $p_1 = 0.60$
- $\alpha = 0.05$ (one-tailed) and
- $\beta = 0.10$

$N=25$ patients should participate in the study to ensure a power of $1-\beta=0.90$ for the discrimination of p_0 and p_1 . According to Fleming the null hypothesis should be rejected if at least

$$r = \left\lceil Np_0 + Z_{1-\alpha} \sqrt{Np_0(1-p_0)} \right\rceil + 1$$

responses are observed (x^* denotes the nearest integer to). With p_0 and N defined as above and $Z_{1-\alpha} = (1 - \alpha)$ -quantile of the normal distribution = 1.645 at least 12 responders should be observed to show the efficacy as postulated.

Using the same approach in the 15 additional patients, submitted to an adapted drug regimen, the power will be 80% to discriminate a $p_0=30\%$ (expected CR rate) from a $p_1=65\%$ (meaningful increase in CR rate), if 8 out of 14 completed patients are considered as responders, with a one-tailed alpha error of 5%.

Alternatively, the power will be 90% to discriminate a $p_0=30\%$ from a $p_1=70\%$ again if 8 out of 14 completed patients are considered as responders, with a one-tailed alpha error of 5%.

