17.1 Appendix 1 – Overview of current relapsed/refractory AML treatment studies

Table 4: Overview of current relapsed/refractory AML treatment studies

Source	Indication	No of patients enrolled (evaluable)	Drug	Dose	ORR (CR / PR)	SD	PFS (months)	OS (months)
Breems et al ⁽¹⁷⁾	Relapsed/refractory AML	667	Cytarabine + daunorubicin or idarubicin	200 mg/m ² 7 days +	46%			
Paciucci et al. ⁽²⁰⁾	Relapsed/refractory AML	49	Cytarabine + mitoxanthrine	100 mg/m ² 7 days + 10 mg/m ² 3 days	50-60%		8	
Harousseau et al. ⁽¹⁹⁾	Relapsed/refractory AML	35	Cytarabine + Idarubicine	1 mg/m ² + 8 mg/m ² 2 days every 12h 6 doses	50-60%		16	
Spadea et al. ⁽²¹⁾	Relapsed/refractory AML	44	Cytarabine + Mitoxanthrone + Etoposid (MEC)	1 g/m ² + 6 mg/m ² + 80 mg/m ² days 1 to 6	55%			
Greenberg et al. ⁽²⁷⁾	Relapsed/refractory AML	63	MEC		17%		10	
		66	MEC + valspardar (PSC388)		25%		9	
Faderl et al. ⁽²²⁾	Relapsed/refractory AML	32	Cytarabine + Clofarabine	1 g/m ² + 40 mg/m ² 5 days	48%			

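### The 30% null rate is labelled the expected CR rate without a source, so rejecting it shows that the combination exceeds 30%, not that Selinexor contributes

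*Protocol*

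**What the plan says.** The Protocol gives p0 two meanings.

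- **A reference rate.** The synopsis (sample size calculation) sets "two response levels p_0 (expected CR rate) and p_1 (meaningful increase in CR rate" at 30% and 60%. Section 8.2 uses the same two labels in its paragraph on the 15 additional patients. An increase over an expected rate reads as an increase over what happens without Selinexor.
- **A futility rate.** Earlier in section 8.2, p0 is the largest response proportion "which, if true, would clearly imply that the treatment does not warrant further investigations". SAP section 5 carries only this meaning.

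Neither document gives a source or derivation for 30%.

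On the decision, section 8.2 says that "at least 12 responders should be observed to show the efficacy as postulated" among 25 patients, and uses 8 of 14 completed patients for the additional cohort. Protocol sections 2.1 and 8.1 and SAP section 6 describe the aim as the efficacy of Selinexor. The trial has a single arm. SAP section 12.1 reports the response rate with a Wilson 95% interval and gives no reference rate for the backbone.

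On the backbone, Table 4 (Appendix 1) has two rows with the trial's drug classes. "Cytarabine + daunorubicin or idarubicin" (667 patients) has 46%, and cytarabine plus idarubicin (35 patients) has 50-60%. Section 1.1.1 adds: "Re-induction with Ara-C and daunorubicin will result in a 50% CR rate in patients who had a first remission lasting longer than 1 year".

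**The concern.** All patients receive Ara-C and idarubicin plus Selinexor. If 30% is taken as the rate expected without Selinexor, passing the rule reads as evidence that Selinexor adds something. The only literature in the Protocol on cytarabine with daunorubicin or idarubicin gives higher rates than 30%. The only Table 4 entries at or below 30% (17% and 25%) belong to a regimen of mitoxantrone, etoposide and cytarabine, with or without a further agent.

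The type I error is calculated at 30%. If the backbone alone does better than that in these patients, the chance that an inactive add-on passes is above 5%. At stake is the sentence the report may write: that the combination is active above 30%, or that Selinexor has been shown to work.

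**Working it through.** **Inputs.** From Protocol 8.2: p0 = 0.30, p1 = 0.60, one-sided alpha 0.05, beta 0.10, n = 25, success at 12 or more; for the additional cohort, success at 8 or more of 14 with p1 = 0.65 or 0.70. From Table 4 and section 1.1.1: 46%, 50-60% and 50%. The rates 34% and 38% are assumptions, chosen to show what happens just above 30%.

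**Reproducing the design.** Fleming cutoff: 25 × 0.30 + 1.645 × √(25 × 0.30 × 0.70) = 7.5 + 3.77 = 11.27; nearest integer 11, plus 1 gives 12. The exact tail is

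P(X ≥ r) = Σ C(n,k) p^k (1−p)^(n−k), summed over k = r to n.

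- 12 of 25: 0.0442 at p = 0.30 and 0.922 at p = 0.60. A search for the smallest n meeting both error limits exactly (the A'Hern criterion) returns n = 25, r = 12.
- 8 of 14: 0.0315 at p = 0.30, 0.816 at p = 0.65 and 0.907 at p = 0.70.

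The stated figures are correct for the p0 and p1 chosen.

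**Chance of passing if Selinexor adds nothing.** The same tail, with p set to the backbone rate:

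| Backbone rate | Basis | P(≥12 of 25) | P(≥8 of 14) |
|---|---|---|---|
| 30% | design p0 | 4.4% | 3.1% |
| 34% | assumed | 10.4% | 6.4% |
| 38% | assumed | 20.4% | 11.6% |
| 46% | Table 4, 667 patients | 49.8% | 28.4% |
| 50% | section 1.1.1; low end of Table 4, 35 patients | 65.5% | 39.5% |

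The cutoff of 12 in 25 is an observed rate of 48%, above the 46% row and below the 50-60% row.

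**Link to the SAP interval.** The Wilson 95% lower limit is 30.03% at 12 of 25 and 32.6% at 8 of 14. These are the smallest counts whose lower limit exceeds 30%, so reading the SAP 12.1 interval against 30% gives the same cutoffs.

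**The case against.** The strongest reply is that the cited rows do not describe this trial's backbone in this trial's patients. Most of that stands.

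- **Dose and schedule.** The trial gives Ara-C 100 mg/m² on days 1-7. The 46% row lists 200 mg/m² for 7 days. The 50-60% row has a 12-hourly, six-dose schedule, and its reference title speaks of intermediate-dose cytarabine.
- **Case mix.** The reference title behind the 46% row concerns first relapse, although Table 4 labels it relapsed/refractory. The 50% in section 1.1.1 is limited to first remissions longer than one year. The trial also admits refractory disease and relapse after transplantation, and section 1.1.1 says the chance of a second remission depends on the length of the first.
- **Endpoint.** The Table 4 column is headed ORR (CR / PR), while the trial counts CR and CRi. This part is weaker. Section 1.1.1 calls the 55% of the mitoxantrone-etoposide-cytarabine row a CR rate. The 48% for clofarabine plus cytarabine equals 12/25, which matches the 7 CR and 5 CRi in 25 patients described there. The heading still leaves doubt. If 46% were 10 points too high (illustration only), the passing chances at 36% would be 14.9% and 8.8%.

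A reader might therefore infer that the Protocol puts the backbone at 46-60% in this population and that the real false-positive rate is 50% or more. The documents do not support that. They leave 30% unsourced; they do not refute it.

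It can also be said that the formal hypotheses concern only a rate against 30%, that a futility rate is a normal phase II benchmark, and that no single-arm trial isolates an add-on's contribution whatever p0 is. That is right, and it is why p0 need not change. It does not answer the reference-rate label or the attribution of a positive result to Selinexor.

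A reader might also take a pooled count from the Wilson interval as a success rule (18 of 40 is the smallest whose lower limit exceeds 30%). Neither document sets a pooled cutoff, so none is used here.

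**Conclusion.** The concern holds as one of labelling and interpretation. The sample size arithmetic is sound, and 30% is usable as a futility rate. It is not supported as the rate expected without Selinexor: no source is given, and the Protocol's nearest evidence, though unmatched, lies higher.

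The size depends on an unknown. With an inert add-on, the 12-of-25 rule passes about 10% of the time at a backbone rate of 34% and 20% at 38%. It reaches 50% or 66% only if the cited 46% or 50% carried over to these patients. The 8-of-14 rule gives 6%, 12%, 28% and 40% at the same rates. A backbone only modestly above 30% is enough to break the 5% rate, so the conclusion does not rest on accepting Table 4. The calculation assumes independent patients, a common rate, and the full 25 or 14 evaluated.

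The SAP addendum counts morphologic leukemia-free state as response. That makes 30% easier to exceed, so the limit on interpretation matters more under that definition.

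**What to change.** Keep p0 and n; enrolment is closed.

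1. In the synopsis and Protocol 8.2, delete the label that calls p0 the expected CR rate. Keep the single definition of p0 as the largest rate that does not justify further study.
2. In Protocol 8.1-8.2 and SAP 6 and 12.1, state that rejecting the null shows only that the CR/CRi rate of the combination exceeds 30%, and that it does not show a contribution of Selinexor. If the addendum's responder definition is used, name it in that sentence.
3. Replace the wording "at least 12 responders should be observed to show the efficacy as postulated" to match: 12 or more responders allow the conclusion that the rate with the combination exceeds 30%.
4. Optionally, show the Wilson interval beside the cited backbone rates as descriptive context, with the dose, case-mix and column-heading caveats. It should not be a test, because the rates are unmatched.

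The cost is wording and, if wanted, one descriptive table row. No patients or data are needed. The downside is a more modest claim.
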